## 3. Study design

### 3.1 Design overview

The proposed open label study is single-center randomized, phase II clinical trial designed to address the following specific aims:

- a) **To optimize an MR protocol to characterize the range and rates of *baseline and dynamic* measures of metabolism and energy homeostasis following an acute IV fructose challenge.** Volumetric and quantitative measures of hepatic lipid deposition, energy levels, and water homeostasis will be characterized in normal volunteers to determine typical ranges and coefficients of variation for each technique.
- b) **To differentiate the baseline and dynamic changes of metabolic and energy homeostasis following an acute IV fructose challenge in patients with biopsy-proven NAFLD.** MR-based measurements from the Aim 1 protocol will be correlated to clinical measures of metabolism, energy homeostasis and histologic disease activity before, during and at 4 and 24 hours following IV fructose challenge in regions co-localized and distant from biopsy.

A cohort study of healthy volunteers (n=30) and patients with NAFLD (n=70) will be enrolled. Healthy volunteers will have no evidence of chronic liver disease (normal liver enzymes and normal liver imaging and/or a liver biopsy performed for clinical evaluation of liver disease but whose pathology results note no pathologic abnormalities). Patients with suspected NAFLD who will undergo a standard-of-care liver biopsy, or who have had a historical biopsy within 6

months of the Screening visit, will have both acute intravenous fructose challenge for assessing baseline and post-dietary intervention *static and dynamic* measures of metabolism and energy homeostasis. Co-localization of liver biopsy with MRI to optimize / assess MRI measures of the histologic features of NAFLD will be performed to develop MRI as a surrogate “biomarker” for liver biopsy. With the exception of the liver biopsy, no accurate non-invasive biomarker for disease activity currently exists.

Screening for eligibility and collection of baseline data will span up to 8 weeks. Patients who have had a liver biopsy showing NAFLD within 6 months of the Screening visit or patients who will be undergoing a standard of care percutaneous liver biopsy for NAFLD will be consented.

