## 9. Trial protocol—Study Visits and Events

### 9.1. Visit schedule overview

***Healthy controls*** will ONLY undergo:

- Screening for eligibility for enrollment (1-2 visits over a maximum of 8 weeks)
- Acute intravenous fructose challenge with measure of metabolism and energy homeostasis by magnetic resonance spectroscopy (MRS) (baseline and assessment of change over 60 minutes).
- MRI of the liver

Data collected from healthy controls will be used as reference and optimization values for which study will assess metabolic and energy homeostatic measures in those with NAFLD.

***Patients with NAFLD*** will undergo the following related activities study phases:

- Screening for eligibility for enrollment (1-2 visits over a maximum of 8 weeks)
- Acute intravenous fructose challenge with measure of metabolism and energy homeostasis by magnetic resonance spectroscopy (MRS) (baseline and assessment of change over 60 minutes. MRI of the liver

- Co-localization of non-invasive MR biomarkers with liver biopsy procedure.

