#### 9.4. Visit Day 0:

Patients with suspected NAFLD, who have not had a biopsy in the prior 6 months, will have a standard of care liver biopsy followed by co-localization of liver biopsy with MR.

Patients will be escorted to the Department of Radiology for baseline MRI/MRS imaging (MRI study protocol and data acquisition sequences detailed in [Appendix A](#)). Time 0 uric acid, insulin, glucose, lipid panel, and free fatty acids will be obtained. IV Fructose will be administered via heplock and dynamic measures of hepatic ATP and other metabolite measures will be obtained over 1 hour. At that time, another venous blood sample will be collected for laboratory evaluation (uric acid, glucose, insulin, lipids, and free fatty acids).

After acquisition of these late hepatic recover ATP measures, for the patients who have not had a historical biopsy in the 6 months prior to screening, a percutaneous liver biopsy will be performed as standard of care. After standard of care procedures and recovery are completed for the percutaneous liver biopsy, a very limited MRI will be performed to co-localize the site of liver biopsy with the exact site of MRI for modeling of non-invasive MRI biomarkers to features of chronic liver disease as characterized on liver biopsy. Subjects with suspected NAFLD may have two MRI's (one for IV fructose challenge and one for co-localization with liver biopsy site). For subjects with NAFLD, study participation will end after completion of the second MRI.

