## 10. Statistical design and analysis

Coefficients of variance (CV) will be used to evaluate reproducibility of MRS/MRI baseline measures. Intra-class correlations (ICC) will be used to measure absolute test-retest baseline measure reliability for the test-retest subjects. ICCs will be calculated with a model that separates subject, voxel, measurement and error variances using an analysis of variance (ANOVA) method. We will include a number of multi-factorial random effects models (66, 67) which use a restricted maximum likelihood (REML) algorithm to prevent negative variance terms. The ANOVA model for metabolite estimates across all subjects will be  $M_{ijk} = \mu + S_i + V_{ij} + N_k + e_{ijk}$  where  $\mu$  is the average across all voxels,  $S_i$  = subject,  $V_{ij}$  = voxel and  $N_k$  = scan random effects, respectively and  $e_{ijk}$  is residual error. For ICC in individual subjects, we leave out the  $S_i$  term. ICCs for test-retest measures will be based on random-effects analysis of the variance models and will be computed as follows:  $ICC = \sigma^2_B / (\sigma^2_B + \sigma^2_w + \sigma^2_e)$  where  $\sigma^2_B$  is generalized between-subject variance of metabolites,  $\sigma^2_w$  is within-subject variance between scans 1 and 2 and  $\sigma^2_e$  is variance due to random noise (68). CVs for test-retest reproducibility will be calculated using  $CV = \sqrt{\sigma^2_w + \sigma^2_e} / \mu$ . Similarly we will obtain CVs from the first 20 subjects in Aim2 and will compare these to the normal population.

Dynamic changes will be characterized in a more *ad hoc* manner. From the metabolite estimates at time  $t$  ( $M_{ijkt}$ ), the following parameters will be measured for each individual (subscript  $i$ ): baseline ( $B_i$  = mean of  $M_{jkt}$ , where  $t$  = prior to fructose challenge), range of change from baseline ( $D_i = B_i - \min(M_{jkt})$  if any), time to maximal change ( $T_i$  = time to reach  $\min(M_{ijkt})$ ), time to baseline recovery ( $R_i$ , if applicable). A 95% confidence interval of baseline will be used to test if the metabolite level is recovered to the baseline. If it does not reach the baseline, we will estimate the baseline based on the assumption of a linear recovery rate. Since metabolite levels will be measured at discrete time points, spline smoothing will be used to fit the curve. These values will be averaged across the cohort of volunteers and simple measures of variance calculated.

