## Appendix A:

### **MRI/MRS Protocols for Assessment of Energy Homeostasis and MR Biomarkers for NAFLD**

In all cases no patient repositioning will need to occur between data acquisitions for different MR nuclei. Primary measures are indicated in blue and include  $^1\text{H}$  MRI/MRS for water and fat measures and  $^{31}\text{P}$  UTE MRS for fructose measures. In all cases, the multiple acquisitions acquired prior to the injection of fructose will serve as test-retest cases for confirming measurement variance in the presence of pathology. Interleaved measures for experimental hypotheses may be moved or removed in order to ensure sufficient primary measures within the allotted MR time slot.

Only MR Slot 1 and Slot 2 protocols shown below will be used on the healthy volunteers for Aim 1 in order to optimize these protocols. The full MR protocol shown below will be performed for NAFLD subjects.

MR Slot 1 (Time 0)	MR Slot 2 (Post biopsy)
<math>^1\text{H}</math> MRI - anatomical $^1\text{H}$ MRI/MRS – water/fat $^{31}\text{P}$ UTE MRS – fructose baseline (multiple acquire) Fructose injection $^{31}\text{P}$ UTE MRS – fructose dynamic (multiple acquire) $^1\text{H}$ EPSI – water/fat $^{31}\text{P}$ UTE MRS – fructose dynamic (multiple acquire)	<math>^1\text{H}</math> MRI - anatomical for biopsy localization $^{31}\text{P}$ UTE MRS – fructose recovery (multiple acquire) $^1\text{H}$ MRI/MRS – water/fat

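### The documents do not say consistently who has 31P recovery data beyond 60 minutes, or when, and the rule for time to recovery depends on the answer

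*Combined protocol and SAP*

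**What the plan says.** Five places bear on late 31P acquisition.

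- **Section 5** has spectra collected for one hour after fructose, with no distinction by group.
- **Section 9.1** lists the only procedures for controls: screening, the challenge with MRS ("baseline and assessment of change over 60 minutes") and a liver MRI. The NAFLD list uses the same 60-minute wording and adds co-localization with biopsy.
- **Section 9.4** puts the late ATP measures at the end of that hour, before the biopsy. After the biopsy, "a very limited MRI will be performed to co-localize the site of liver biopsy"; 31P is not mentioned. The biopsy is for patients without one in the 6 months before screening. NAFLD participation ends after the second MRI.
- **Section 3.1(b)** speaks of measures in NAFLD "before, during and at 4 and 24 hours following IV fructose challenge".
- **Appendix A** states: "Only MR Slot 1 and Slot 2 protocols shown below will be used on the healthy volunteers for Aim 1". It adds: "The full MR protocol shown below will be performed for NAFLD subjects". The table shows the same two slots for both. The second is headed "MR Slot 2 (Post biopsy") and includes 31P spectra labelled "fructose recovery (multiple acquire").

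Section 10 defines R_i as time to baseline recovery, judged by the 95% confidence interval of baseline. When recovery is not seen: "If it does not reach the baseline, we will estimate the baseline based on the assumption of a linear recovery rate". It sets no common observation window and no censoring rule.

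**The concern.** Section 3.6 makes the rate and extent of the dynamic changes primary, and section 10.2 plans to compare healthy volunteers with NAFLD. R_i is the section 10 parameter that describes how long recovery takes. Section 2.3 cites delayed ATP recovery in a small NAFLD pilot (n=8) as part of the rationale.

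The rule for R_i does not give the same answer under different windows. A participant with spectra only to 60 minutes who has not recovered gets a linear projection. A participant with a later session gets a value read across the gap to that session. If late data follow group, or biopsy timing within NAFLD, identical physiology can yield different R_i. If controls stop at 60 minutes and NAFLD patients have a late slot, the error can make NAFLD recovery look slower, which is the direction that the study expects.

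**Working it through.** The plan states no figure for R_i, so there is none to reproduce. The check sets the schedules side by side and then applies the section 10 rule to one assumed curve.

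**1. Who has 31P data after 60 minutes?**

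| Source | Controls | NAFLD, biopsied on Day 0 | NAFLD, historical biopsy |
|---|---|---|---|
| 5 and 9.1 | No | No | No |
| 9.4 | Not covered | Co-localization MRI; 31P not mentioned | No post-biopsy MRI |
| 3.1(b) | Not covered | 4 h and 24 h | 4 h and 24 h |
| Appendix A | Yes (Slot 2), time undefined | Yes (Slot 2), no clock time | Slot 2 under the full protocol, but no study biopsy to time it from |

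Section 8.2 also admits patients with a prior clinical or histological diagnosis and no recent biopsy. The 24-hour measure in 3.1(b) is also hard to square with participation ending after the second MRI in 9.4.

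**2. Extrapolation error on 60-minute data.** The 20% fall is borrowed from the change assumed in section 10.1. The rest is assumed: nadir at 10 minutes, exponential recovery with constant τ, and recovery declared within 2% of baseline.

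- True time: R = 10 + τ·ln(0.20/0.02) = 10 + 2.303τ
- Deficit at 60 minutes: d = 0.20·exp(−50/τ)
- Mean slope from 10 to 60 minutes: s = (0.20 − d)/50
- Linear projection: 60 + (d − 0.02)/s to the 2% band, or 60 + d/s to full baseline

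τ = 40:
- R = 10 + 92.1 = 102 min
- d = 0.0573 and s = 0.00285 per min
- Projection = 60 + 13 = 73 min, or 60 + 20 = 80 min
- Shortfall 22 to 29 min

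τ = 60:
- R = 10 + 138.2 = 148 min
- d = 0.0869 and s = 0.00226 per min
- Projection = 60 + 30 = 90 min, or 60 + 38 = 98 min
- Shortfall 50 to 58 min

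**3. When there is no error.** Recovery falls within the hour if 10 + 2.303τ ≤ 60, that is τ ≤ 21.7. At τ = 20, R is 56 minutes with or without a late slot.

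**4. What a late slot would do.** A late session does not return the true value either, because R_i is then interpolated across the gap. With a single late session at an assumed 240 minutes (the 4 hours of 3.1(b)), same curve and 2% band:

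| τ (min) | True R | 60-min data only | With 240-min session |
|---|---|---|---|
| 30 | 79 | 65 | 145 |
| 45 | 114 | 77 | 188 |
| 60 | 148 | 90 | 206 |
| 90 | 217 | 116 | 232 |

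Moving the session to 120 minutes at τ = 45 gives about 117 instead of 188. The gap between schedules is therefore set largely by a time that the documents do not give.

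**5. Simulated false positives with no true difference.** Setup: 30 controls with 60-minute data, 70 NAFLD patients who all have a 240-minute slot, spectra every 5 minutes, 6 baseline scans, a moving average in place of the unspecified spline, and a two-sided 5% Mann-Whitney test.

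| Median τ (min) | Measurement CV 2% | Measurement CV 5% |
|---|---|---|
| 20 | 26% | 4% |
| 45 | 100% | 45% |
| 90 | 100% | 98% |

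With equal 60-minute windows the rate is 3.5% to 6.8%. Giving every NAFLD patient a late slot makes the unequal-window figures an upper bound on that point.

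**The case against.** A reader might infer that controls and NAFLD patients are scheduled differently, so that unequal windows are built into the design. The documents do not establish that. The Appendix A sentence gives controls the same two slots that the table shows for NAFLD. Sections 5 and 9.1 give both groups one hour, and 9.4 places the late ATP measures inside it. On those sections alone the windows are equal. The contrast in Appendix A between two slots for volunteers and a full protocol for NAFLD hints at more, but the table may be incomplete as extracted and cannot settle the matter.

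A reader might also take the 22 to 29 minute shortfall as the difference between groups. It is not: it measures linear projection against an assumed truth, and step 4 shows that a late slot does not recover that truth.

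Other objections also stand in part. Section 10 names no between-group test of R_i; the comparison is inferred from 3.6 and 10.2. It calls the dynamic parameters ad hoc, and section 3.5 calls the study exploratory. Its wording refers to estimating the baseline, so applying the linear rule to R_i is an interpretation. Depth of fall (D_i) and time to maximal change (T_i) are unaffected if the nadir falls within the hour.

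None of this supplies what is missing: one statement of who has late spectra and at what time, and a rule that makes R_i comparable when some do and some do not.

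**Conclusion.** The point holds as an internal inconsistency with a possible, conditional bias. Sections 3.1(b), 9.1, 9.4 and Appendix A cannot all be followed, Slot 2 has no defined time in controls, and section 10 has no common window. Bias in R_i arises only if some participants have late spectra and others do not (or have them at different times), and recovery is incomplete at 60 minutes. The split may run between groups or, within NAFLD, by biopsy timing.

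The size cannot be stated from the documents. The illustrated extrapolation error is 22 to 29 minutes at τ = 40 and 50 to 58 at τ = 60, and essentially nil at τ = 20. The kinetics, the 2% band (section 10 uses the baseline confidence interval, whose width is not given) and the late-slot times are all assumptions. The simulated rates show direction and possible range, not an expected error rate. This should be corrected before any analysis of R_i; confidence is medium.

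**What to change.** 1. Reconcile sections 3.1(b), 9.1, 9.4 and Appendix A on who has 31P spectra after the first hour, what that session contains, and its clock time after fructose, including for controls and for NAFLD patients without a Day 0 biopsy.
2. In section 10, for the healthy-versus-NAFLD comparison and for comparisons within NAFLD, compute R_i from the first 60 minutes, which sections 5 and 9.1 give to every participant. Treat non-recovery by 60 minutes as censored instead of projecting linearly.
3. Report later 31P data separately and descriptively, with the actual acquisition times.

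The cost is wording plus one analysis rule; no added scans are needed. The downside is that late points leave the group comparison, so differences that appear only after the first hour would be described and not tested. A single clock-time schedule for both groups would keep those points, but it means settling and delivering the same late session for everyone.
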